active members) by mass mailing to the full cohort of an IRB-approved letter describing the study, followed by phone calls to invite questions. Although this cohort is an epidemiological outcome cohort, and the initial opinion was that this duration of intervention was inappropriate for such a study, funding pressures have influenced the CACTI PI to consider mechanistic studies and to agree that a short term metformin intervention is acceptable. In fact, a large grant to expand upon this pilot study is currently pending with the NIH. A strength of this study is thus access to the existing NIH-CACTI cohort that has been prospectively studied for ≥ 6 years. This is an active cohort with a great interest in diabetes and its management, and recruitment of 90 subjects for our recent clamp sub-study was easily accomplished.

Study population: The goal is to complete 30 T1D subjects (50% male in each group) for the pilot study. We expect to screen up to 100 subjects to enroll 40 and complete 30. Inclusion criteria:(1)age 20-59 years of age, (2) type 1 diabetes based on antibody-positivity, rapid persistent conversion to insulin requirement after diagnosis, absent C-peptide, or DKA at diagnosis, or a clinical course consistent with T1D, (3) HbA1c 6.0-9.5 (4) willing/able to commit to two 6 week-long study phases, each consisting of blinded medication with blinded CGM, frequent phone follow-up, and 3 days of prescribed diet followed by hyperinsulinemic euglycemic clamp, vascular testing, and 2 muscle biopsies. Exclusion criteria include:

[figure not shown]
- Any comorbid condition associated with inflammation, IR, or dyslipidemia
- Tobacco use
- Pregnancy
- Steroid use
- Scheduled vigorous physical activity >3 days a week
- Angina, known CAD, or any other cardiovascular or pulmonary disease
- A history of COPD or asthma
- Presence of systolic blood pressure >190 at rest or >250 with exercise or diastolic pressure >95 at rest or >105 with exercise
- Untreated thyroid disease
- Proteinuria (urine protein >200 mg/dl) or a creatinine ≥ 1.5 mg/dl(males) or 1.4 mg/dL (females), suggestive of severe renal disease
- Proliferative retinopathy.
- Niacin treatment
- Administration of experimental agent for T1D within 30 days prior to screening
- Recent (prior 6 months) or current metformin or thiazolidinedione use
- Hypoglycemia unawareness or recurrent severe hypoglycemia (no symptoms of hypoglycemia with FSBS<40 and episodes of this severity >1 per week)

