- Weight instability (weight change >5% in last 6 months)
- History of any organ transplant, including islet cell transplant
- Current or prior infection with HIV, hepatitis B or hepatitis C, or transaminases >2x ULN
- Any condition, medical or otherwise that would, in the opinion of the investigator, prevent complete participation in the study, or that would pose a significant hazard to the subject
- History of substance abuse within the 12 months prior to screening

Screening: A phone screen will be followed by provision of the consent form and a screening/enrollment visit at the outpatient CTRC. This visit will include the consent process, history, physical exam, non-fasting screening labs [β -HCG, HbA1c, metabolic panel, TSH, urine microalbumin, and CBC], detailed menstrual history for women, and a DEXA scan for body composition and estimation of caloric needs.

Study design:

T1D subjects (n=30) will have a fixed order of treatment (placebo-metformin) and will be given their first medication after screening is complete and eligibility confirmed. Medications (metformin 500, 1000mg and identical placebo) will be dispensed by the pharmacy and the subject will be blinded to the fixed order of the medications to avoid biased treatment effects throughout the intervention period. As in previous Barbara Davis Center (BDC) metformin studies, this study will use the CTRC pharmacy to dispense the active drug and placebo. Both are provided by Caraco manufacturer. My colleagues at the BDC already purchased tooling for the Caraco brand placebo tablets and the company has agreed to make more placebo tablets for this study as necessary to cut out the upfront cost of tooling.

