Subject discontinuation criteria: (1) Failure to tolerate uptitration to a dose of metformin of at least 500 mg BID within 4 weeks, (2) Patient report of increased hypoglycemia not resolved with insulin dose adjustments within 2 days, (3) Other events or adverse reactions that are possibly related to study drug, that are contraindications to study drug, or that interfere with study measures.

Protocol stopping rules: Occurrence of any severe adverse reaction including but not limited to hypoglycemia leading to unconsciousness or requiring external assistance will immediately be discussed with the data safety officer to evaluate need for protocol termination. Occurrence of more than one such event will lead to an immediate discontinuation of the protocol.

D. Description, Risks and Justification of Procedures and Data Collection Tools:

Methods: All measures will be assessed post 6 weeks of each of two blinded study drugs (metformin and placebo).

Continuous glucose monitoring: Subjects will have continuous glucose monitoring (CGM, (DexCom 7-plus® system)) through both intervention periods. This will be real-time during the first four weeks (insulin dose adjustment and increased safety) and blinded during the last two weeks (statistical adjustment for changes in glycemic control).

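### The hypoglycemia exclusion grades severity by a glucose value, symptoms and a weekly count, so a symptomatic subject with infrequent episodes that caused unconsciousness or needed assistance is not excluded by it

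*Combined protocol and SAP*

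**What the plan says.** Section IV.B, Study population, introduces its list with "Exclusion criteria include" and contains one bullet specific to hypoglycemia: "Hypoglycemia unawareness or recurrent severe hypoglycemia (no symptoms of hypoglycemia with FSBS<40 and episodes of this severity >1 per week". A later bullet excludes any condition that the investigator judges would prevent full participation or "that would pose a significant hazard to the subject"; it does not name hypoglycemia.

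The Screening paragraph describes Visit 1: "This visit will include the consent process, history, physical exam, non-fasting screening labs". It does not itemize a question on past hypoglycemia.

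The Protocol stopping rules paragraph covers any severe adverse reaction and gives as an example "hypoglycemia leading to unconsciousness or requiring external assistance". Such an event goes at once to the data safety officer. Then: "Occurrence of more than one such event will lead to an immediate discontinuation of the protocol". Separately, the Subject discontinuation criteria allow withdrawal for increased hypoglycemia that insulin adjustment does not resolve within 2 days, and for "Other events or adverse reactions that are possibly related to study drug".

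On numbers, the Study population paragraph says: "We expect to screen up to 100 subjects to enroll 40 and complete 30".

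**The concern.** The entry bullet and the stopping rule grade severity on different scales. At entry, severity is a finger-stick value below 40, with absent symptoms and a frequency above one a week. On study, it is the consequence of the episode. The bullet's label shows that a history of severe hypoglycemia was meant to count at entry, but its definition misses the kind of history that the stopping rule itself treats as severe.

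The trial adds metformin to insulin, and section IV.D (Risks, Metformin) acknowledges a hypoglycemia risk, mainly at the start and during uptitration. A subject with a recent assisted episode is one for whom the entry decision should be explicit. As written, it rests on whether the investigator asks and how the general hazard bullet is then applied.

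A lesser point is wording: the label joins two conditions with an or, while the parenthesis joins their definitions with an and.

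**Working it through.** The plan states no figure on this point, so there is nothing to reproduce. The check is logical.

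**Inputs** (exclusion bullet). A = no symptoms at FSBS below 40. B = episodes below 40 more than once a week. Crossing them gives 2 × 2 = 4 groups.

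**Possible readings.**
- Paired: each label takes its own definition, so A or B excludes.
- Joint: the and is taken literally, so A and B are both required.
- Narrow paired: the severity in the second definition is taken to include absence of symptoms, so the rule is A or (A and B), which reduces to A.

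| Group | Paired | Joint | Narrow paired |
|---|---|---|---|
| No symptoms, more than 1/week | excluded | excluded | excluded |
| No symptoms, 1/week or fewer | excluded | admitted | excluded |
| Symptoms, more than 1/week | excluded | admitted | admitted |
| Symptoms, 1/week or fewer | admitted | admitted | admitted |
| Groups excluded | 3 of 4 | 1 of 4 | 2 of 4 |

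The last group is admitted on every reading. Consequence appears in neither A nor B, so this holds whatever the episodes led to. These are counts of logical groups, not of subjects. The paired and joint readings differ on 3 − 1 = 2 groups.

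**Against the stopping rule.** Its example, unconsciousness or need for outside help, can occur in the last group. The other listed exclusions do not mention hypoglycemia, so only the hazard bullet could catch such a subject, at the investigator's discretion.

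**Screening cost of a consequence-based criterion.** Inputs: up to 100 screened and 40 enrolled (Study population), which leaves room for 100 − 40 = 60 failures. Let f be the fraction of otherwise eligible subjects who would fail the new criterion. The documents give no value for f, so 5%, 10% and 20% are assumptions. The number of otherwise eligible subjects needed is 40/(1 − f), rounded up.
- f = 5%: 40/0.95 = 42.1, so 43; 3 more failures, room for 57 others.
- f = 10%: 40/0.90 = 44.4, so 45; 5 more failures, room for 55 others.
- f = 20%: 40/0.80 = 50; 10 more failures, room for 50 others.

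The nearest figure in the documents is the CGM percentage below 70 in Table 3 (16.2 ± 11.9). It gives no rate below 40 and none for assisted events, so it cannot supply f.

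**The case against.** The strongest reply is that the gap is narrow and already has a backstop. Unaware subjects and those with frequent lows are excluded on the natural reading. Visit 1 takes a history and physical, the hazard bullet is available, and in a small pilot the principal investigator reviews glucose data weekly and adjusts insulin. CGM is real-time for the first four weeks, which include the start and the nominal uptitration. Symptom-prompted checks suit a subject who has symptoms, and individual discontinuation rules apply. Entry criteria also need not mirror stopping rules. All of this stands and limits the importance of the point. It does not close the gap: the hazard bullet is discretionary, and the other measures, apart from the Visit 1 history, act after enrollment.

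Three stronger readings are tempting and are not supported.
- A reader might infer that hypoglycemia is the event that stops the protocol. It is one example under a wider class of severe adverse reactions, and the mandatory stop needs more than one event. Whether an insulin-related episode in the placebo phase counts as an adverse reaction is not spelled out.
- A reader might infer that the or/and mismatch means unaware subjects will be admitted. The two labels and two definitions run in matching order, the joint reading would empty the label's or of meaning, and nothing shows that anyone applies it. This part is mainly wording.
- A reader might infer that closing the gap would reduce on-study events or the chance of early termination. The documents give no event rate and no link between history and later events.

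The screening margin also deserves caution. The Recruitment paragraph speaks of enrolling 100 eligible subjects to start 40, which does not match screening 100 to enroll 40; the room for 60 failures rests on the latter.

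**Conclusion.** The point holds as a cheap improvement. On every reading, the bullet admits a symptomatic subject with no more than one episode a week, including one whose episodes led to unconsciousness or external assistance. That conclusion rests on the text alone and needs no assumed rate. The number of such subjects cannot be derived, and the screen-failure figures above only illustrate an assumed range. The gain is a clearer and safer entry screen. No endpoint, analysis or power figure is affected.

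**What to change.** Replace the bullet with three criteria, any one of which excludes:
1. Hypoglycemia unawareness, defined as now by absent symptoms at FSBS below 40. Add no look-back: the present wording has no time limit, and a new window would readmit subjects whose unaware episodes fell before it.
2. FSBS below 40 more than once a week, with or without symptoms.
3. Any hypoglycemia with unconsciousness or requiring external assistance in the prior 6 months, the window already used for metformin use and weight change. Ask this in the Visit 1 history.

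The stopping rule can stay as written.

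The cost is an eligibility wording change, one history question at a visit that already takes a history, and a probably small number of added screen failures that the documents do not allow to be estimated. If the paired reading is already applied, criteria 1 and 2 only restate it and criterion 3 alone adds failures. If a narrower reading is applied, criteria 1 and 2 may add some too.

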 - arterial stiffness (PWV and AI),
 - CGM measures of hyperglycemia, hypoglycemia, and glycemic variability for one week prior to each clamp,
 - Metabolic (NEFA, lipids, insulin, glucose), inflammatory (IL-6, TNF- α , hsCRP, adiponectin), thrombotic (PAI-1), oxidative stress (urinary isoprostanate, TBARs), and endothelial (ICAM, endothelin-1) markers at baseline each study day,
 - Counter-regulatory hormones (cortisol, growth hormone, glucagon, and catecholamines prior to each clamp,
 - Respiratory quotient at baseline and after low dose insulin infusion,
 - Heart rate variability,
 - Mitochondrial content (DNA and electron transport chain complexes),
 - Mitochondrial function (carbohydrate and lipid oxidation, max state 3 O₂ consumption, uncoupled O₂ consumption),
 - Mitochondrial state 3 O₂ consumption,
 - Mitochondrial oxidant generation (H₂O₂ production, glutathione redox state), and
 - Mitochondrial ATP production/ADP depletion by 31P-MRS.

[figure not shown]
B. Description of Population to be Enrolled: Study Design and Research Methods

Hypotheses: Metformin will improve (1) insulin action, (2) vascular function and compliance, and (3) mitochondrial function and oxidant generation in T1D subjects supporting a therapeutic role for metformin in T1D management, including CVD risk management.

Specific Aims: **Specific Aim 1:** Determine the effect of metformin on IR in T1D. **Specific Aim 2:** Determine the effect of metformin on vascular correlates of IR. **Specific Aim 3:** Determine the effect of metformin on mitochondrial function and oxidant generation.

Overall research plan: I propose to address these hypotheses and aims with a single-blinded, fixed-order, placebo-controlled cross-over design study in T1D subjects. The intervention will consist of 6 weeks of treatment with metformin, separated from the placebo period by a \geq 2 weeks washout period. The fixed order is needed because we and others have found persistent residual effects from metformin treatment, and the necessary washout period is not known. Metformin has been studied to a limited degree in T1D, primarily in terms of glycemic control. It has been found to be safe and well-tolerated in these studies (Vella) and the proposed dose and duration have precedent in the literature. [name] at this institution has performed a study using metformin in T1D youth. From his contact with the FDA, an IND is not required for this study.

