Subjects will be instructed to take study drug at 500mg at bedtime for the first week, 500 mg twice daily for the second week, 500/1000mg daily for one week and 1000mg twice daily for the remainder of the 6 week period. Subjects who fail to tolerate an uptitration will be held at the prior dose for an additional 3 days and then retried. Subjects who have not reached at least 500 mg BID dosing by the end of week 3 will be withdrawn from the study. Thus, final metformin dosing will be 500 BID or 1000 BID. During the last three days of each treatment phase, subjects will be placed on a standardized typical diabetic diet (40% carbohydrate, 35% fat, 25% protein; based on CACTI food records) for three days prior to late evening admission on day 3 to the CTRC. Overnight admission is critical to ensure that all subjects are in the same state prior to each testing session. Remaining pills will be turned in to allow a pill count as a measure of compliance. Subjects will be transitioned to an insulin drip for overnight glucose control using the protocol previously used for CTRC protocol 1499 (see appendices for starting doses and titration schedule). Inpatient studies (baseline labs, vascular studies, biopsies, and hyperinsulinemic euglycemic clamp) will be performed the following day (Figure 4). After a two week to two month washout period, the full cycle will be repeated with the second intervention. Women will be tested at the same time in their menstrual cycle (day 4-9) after each intervention period. Allowing up to 2 months between interventions is necessary to allow this type of scheduling with the possibility of a missed cycle due to scheduling conflicts. The study timeline and detailed visit schedule are as follows:

Screening:

- Visit 1: Screening visit - consent process, H&P, non-fasting labs, DEXA, dietary questionnaire

Stage 1 (Study drug A, Placebo):

- Visit 2: Stage 1 start visit (day A1) – Insert CGM and receive instruction on use and download, pick up Placebo, Instructions from PI re med dosing and insulin dose self-adjustment
- Visit 3: Stage 1 CGM follow-up visit (day A8) – in person CGM download and reinsertion of sensor for the next week. Review glucoses with PI.
- Visit 4: Stage 1 prestudy day visit (day A39) – pick up three day diet and receive instructions on insulin dosing and times for the pre-study day. Accelerometer set-up
- Visit 5: Admission for Placebo study day (Days A42, 43) – see below

2 weeks- 2 months wash-out

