Stage 2 (Study drug B, Metformin):

- Visit 6: Stage 2 start visit (Day B1) - Insert CGM and receive instruction on use and download, pick up Metformin, Instructions from PI re med dosing and insulin dose self-adjustment
- Option for one week visit 6b if desired for first repeat CGM insertion
- Visit 7: Stage 2 prestudy visit (Day B39) - pick up three day diet and receive instructions on insulin dosing and times for the pre-study day. Accelerometer set-up
- Visit 8: Admission for Metformin study day (Days B42,43) - see below

During the study visits procedures will include the following: baseline blood draws for inflammatory, metabolic, endothelial, and thrombotic markers; heart rate variability; vascular function and stiffness by flow-mediated dilation (FMD), plethysmography, brachial artery distensibility, and pulse wave velocity (PWV), and augmentation index (AI); insulin sensitivity by 2-stage hyperinsulinemic clamp (8, 40 mU/m²/min) with glucose tracer; muscle biopsies preclamp. If blood sugar at start of the tracer infusion and of the clamp is <60 or >180, the study visit will be concluded without the clamp.

³¹P-MRS optional substudy: DRI pilot funding has been obtained to add a ³¹P-MRS study (method described further below) to the late afternoon preceding each admission to the CTRC for 10 of the MeT1 subjects. On recruitment into MeT1, subjects will be given the option to enroll in this additional sub-study. Specific exclusion criteria for this sub-study will include presence of any metal or other contraindications to MRS, including significant claustrophobia. A separate opt-in section in the consent form will be prepared and submitted to the IRB for this sub-study. Once 10 subjects have opted in and completed, the sub-study will be considered complete and closed to further enrollment. At that point, an interim analysis, including unblinding of these 10 subjects, will be performed. Those who opt in to the sub-study will follow the original study design exactly, with the exception that on day 3 of their study diet, they will be asked to present to the UCD Brain Imaging Center (behind the Leprino Building) in the late afternoon (fasting since lunch; 4-6 hours) for the MRS scan and then proceed to the CTRC for admission for the full study day the following day.

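### The MRS sub-study interim plans to unblind 10 subjects in a trial where everyone has the same treatment order; the analysis does not need it, and it puts the subject blind at avoidable risk

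*Combined protocol and SAP*

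**What the plan says.** Section IV.B, Overall research plan, describes a "single-blinded, fixed-order, placebo-controlled cross-over design study". Under Study design in the same section, all subjects take placebo first and metformin second, and "the subject will be blinded to the fixed order of the medications"; the stated purpose is to prevent biased treatment effects. Study drug in section IV.D repeats the fixed order and the single blind. No blinded tester, reader or analyst is described.

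The visit schedule names the drug at each stage. At the stage 1 start visit subjects "pick up Placebo, Instructions from PI re med dosing and insulin dose self-adjustment", and at the stage 2 start visit they "pick up Metformin, Instructions from PI re med dosing and insulin dose self-adjustment".

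The paragraph on the 31P-MRS optional substudy in section IV.B says: "Once 10 subjects have opted in and completed, the sub-study will be considered complete and closed to further enrollment". It then says that at that point "an interim analysis, including unblinding of these 10 subjects, will be performed". It does not say which outcomes are analysed, who is unblinded, who sees the results or what decision follows. Sub-study subjects otherwise follow the main design, so their GIR and FMD data exist by then. The 31P-MRS methods in section IV.D give the sub-study its own primary outcomes, QMax and ADP depletion half-time. The Data Analysis Plan (section IV.F) does not mention an interim.

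**The concern.** In a randomised crossover, unblinding 10 subjects says nothing certain about the others. Here the concealed fact is a single one, the order, and all subjects share it. Whoever learns it for one subject knows it for all.

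The subject blind matters because subjects adjust their own insulin in both stages and are asked to keep their activity stable. If subjects still on study learned which stage is placebo, a change in behaviour between stages would fall entirely on the treatment contrast. With a fixed order, treatment and period are fully confounded, so no later analysis could remove it.

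The second issue is scope. Because the sentence does not name the interim outcomes, it leaves open a look at the two primary outcomes, GIR and FMD, for which no alpha is set aside.

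**Working it through.** **Does the interim need unblinding?** The primary analysis compares the post-placebo with the post-metformin value within each subject. Stage 1 is placebo and stage 2 is metformin for everyone, and the schedule says so. The stage label is therefore the treatment label, and the investigator, who gives instructions at both start visits, already works from that schedule. Unblinding gives the analysis nothing new. The only people described as not knowing the order are the subjects.

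**How many subjects could be exposed?** The 10 have finished both stages, so their own data are safe. The exposure concerns later subjects. Inputs: 40 starters and 30 completers (section IV.B, Study population), so the planned loss is 1 − 30/40 = 25%. The opt-in rate is not given and is assumed below.

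Starters needed for 10 sub-study completers = 10 / (opt-in × completion); later starters = 40 − that number.

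| Assumption | Starters needed | Later starters |
|---|---|---|
| 100% opt-in, no loss | 10/(1 × 1) = 10 | 30 |
| 100% opt-in, 25% loss | 10/(1 × 0.75) = 13.3 | about 27 |
| 50% opt-in, 25% loss | 10/(0.5 × 0.75) = 26.7 | about 13 |
| One-third opt-in, 25% loss | 10/(0.333 × 0.75) = 40 | 0 |

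This treats starters as sequential. Subjects who declined the sub-study and are still in treatment when the tenth completer finishes would add to the lower counts.

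**What if a primary outcome were tested at the interim?** The plan gives no figure for the interim, and it states neither alpha nor sidedness. Its power statement for insulin sensitivity (difference 0.5, SD of difference 1, n=30, 75%) is reproduced at 75.4% by a paired t-test at two-sided 0.05, so that level is used here.

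- The statistics at n=10 and n=30 have correlation √(10/30) = 0.577.
- Type I error with success allowed at either look = 1 − P(|Z₁| ≤ 1.96 and |Z₂| ≤ 1.96) = 0.088.
- One million simulated paired t-tests, with t critical values on 9 and 29 degrees of freedom, give 0.089.
- If no claim and no stopping decision can follow from the interim, the error stays at 0.05.

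A test at n=10 would also say little: power for the plan's insulin-sensitivity effect is 29%.

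**The case against.** The sentence treats unblinding as part of an analysis and does not say that subjects are told anything. Harm needs two steps that the text does not state: the 10 learn their order, and the information then reaches subjects still on study. The word may be no more than a formality. This stands, and it makes the point a risk rather than a planned disclosure. But only subjects are described as blind, so read literally the unblinding can only mean telling them.

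A reader might infer that the blind is the sole safeguard against behaviour changing between stages. It is not. The protocol also has a standardized three-day diet, overnight admission on an insulin drip, weekly review of CGM or glucometer data with insulin adjustment, an emphasis on stable activity, and a planned model adjusting for CGM parameters that differ between periods. Subjects are also advised that they may need less insulin on metformin, so the blind may already be imperfect. The added loss is smaller for these reasons, but the blind remains a safeguard on which the protocol expressly relies.

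A reader might also infer that the trial has an uncontrolled efficacy interim with an 8.9% error rate. The documents do not support this. The sentence sits in the MRS paragraph, the sub-study has its own primary outcomes, the protocol stopping rules concern safety only, and no claim is attached to the interim.

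**Conclusion.** The point holds as an avoidable risk to the subject blind, with a secondary gap in the scope of the interim. The planned unblinding serves no analytic purpose, and if it reaches the 10 subjects it gives them the one fact concealed from everyone still on study. Any bias that followed could not be separated from the metformin effect. Its size cannot be estimated from the documents.

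Exposure ranges from none to 30 of 40 starters according to the unstated opt-in rate. The figure of 30 is an upper bound that needs full opt-in and no loss among the first 10; it is not an expectation. About 27 and about 13 are the figures at full and at an assumed 50% opt-in, with the planned 25% loss.

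The 8.9% is conditional: it needs a test of GIR or FMD at 0.05 at both n=10 and n=30, with a claim allowed at either. The likely intent is an MRS-only interim, and the text should say so.

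**What to change.** In the 31P-MRS optional substudy paragraph, strike the clause on unblinding and replace the interim sentence with wording to this effect:

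> After 10 sub-study subjects have completed both stages, only the MRS outcomes (QMax and ADP depletion half-time) will be analysed. GIR and FMD will not be tested at that point. Neither the treatment order nor results by stage will be disclosed to any subject until the last subject has finished stage 2.

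Add a matching line to the Data Analysis Plan, which does not mention the interim. The cost is protocol wording, and the one downside is that the 10 sub-study subjects learn their order later. Blinding of the staff who test or read outcomes is not part of this change: the protocol describes none, and it would be a new design feature.
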